Given most studies regarding the effectiveness and safety of the early follicular phase full-dose down-regulation protocol are retrospective studies, the results may be biased by several confounding factors. Therefore, we would like to conduct a multicenter, randomized controlled trial to compare the pregnancy outcome and safety between the early follicular phase full-dose down-regulation COH protocol and the luteal phase down-regulation protocol.

Methods/Design

We will perform the multicenter, randomized controlled trial in 14 reproductive medicine centers all over mainland China. Included patients will be distributed in a 1:1 ratio to the intervention (early follicular phase full-dose down-regulation) group and the control (mid-luteal phase down-regulation) group. Their live birth rate of fresh embryo transfer and other secondary outcomes will be compared. This study has been approved by the institutional review boards at all study sites. Each participant will sign the consent form before inclusion. Reporting of the study results will follow the 2010 CONSORT statement [11].

Inclusion criteria

The following are the inclusion criteria for this study:

1. Women aged between 20 to 38 years old and with a history of infertility (fail to get pregnant after over one year's regular, unprotected sex), who receive IVF/ICSI for one of the following reasons:
 - ① Tubal factor: e.g. peritubal adhesions, tubal obstruction, etc.. Patients with hydrosalpinx can be enrolled after salpingectomy or tubal ligation;
 - ② Male factor: e.g. oligospermia, asthenozoospermia, teratozoospermia, etc.;
 - ③ Unexplained infertility: patients with a history of infertility more than 1 year but with no specific cause for infertility (ovulation, tubal, endometrial and male factor), or still not get pregnant after the above-mentioned causes being removed.
2. Women with a normal ovarian reserve according to: ① basal steroid hormone on day 2-4 of menstrual cycle: basal FSH≤10mIU/ml, estradiol (E2) <50pg/ml; ② anti-Müllerian hormone (AMH)≥1.1ng/ml; ③ antral follicle count (AFC) ≥7;
3. Women who start their first IVF/ICSI cycle;
4. Women who met the above-mentioned criteria and have given the informed consent.

Exclusion criteria

1. Women with a negative reproductive history, including a history of:
 - ① recurrent miscarriage: women with twice and more than twice spontaneous miscarriage, missed abortion, biochemical pregnancies, etc.;

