2) *Control group* (luteal phase long down-regulation group)

Patients have an injection of short-acting triptorelin acetate (Decapeptyl®, Ferring, Germany) 0.1mg every day, 10-12 days before the menstruation and receive the endocrinology and ultrasound examinations 14-21 days thereafter. If complete pituitary down-regulation is achieved (endometrial thickness≤5mm, basal FSH≤5mIU/mL, LH≤5mIU/mL, E2≤50pg/mL) and the diameter of follicles between 4-6mm under ultrasound,

a supplementation of recombinant FSH (Gonal-F®, Merck, Switzerland) will be given according to the participants' BMI ($18 \leq \text{BMI} \leq 22$, starting dose 112.5IU/d; $22 < \text{BMI} \leq 25$, starting dose 150IU/d).

2. *Ovarian response monitoring and gonadotropin dose adjustment:* 4 days after the daily injection of rFSH, the physician will perform ultrasound to monitor the follicular growth, measure the serum hormone level and adjust the dose of exogenous gonadotropins accordingly.

Trigger and oocyte retrieval

1. *hCG trigger for final oocyte maturation:* When the desired follicle size is reached (at least one follicle ≥ 19 mm or two follicles ≥ 18 mm or three follicles ≥ 17 mm), 250 μ g recombinant human chorionic gonadotropin (HCG) (Luveris®, Merck, Switzerland) will be administered subcutaneously.
2. *Oocyte retrieval:* Oocyte retrieval will be performed transvaginally 36-38 hours after pre-ovulatory hCG injection under ultrasound monitoring.
3. *In vitro fertilization and embryo culture:* Oocyte retrieved will be cultured in vitro for 3-6h before being fertilized via IVF or ICSI. Two top-quality Day 3 cleavage embryos will be transferred 72h after retrieval. If more than 15 oocytes are retrieved, the participant should receive ultrasound examination on the day of embryo transfer. For those complaining abdominal or stomach distension, with an ovary ≥ 7 cm in diameter, estradiol ≥ 4500 pg/ml, there is a high risk of developing moderate or severe OHSS, and all the embryos should be frozen.

Embryo transfer and luteal phase support

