For those not receiving a fresh embryo transfer (e.g. due to OHSS), and those not achieving live birth and with surplus cryopreserved embryos, the outcome of frozen-thawed embryo transfer cycles will be followed up and recorded as well.

Outcome measurements

Primary outcome

The primary outcome of this study is live birth rate per transferred cycle, defined as delivery of any viable infant ≥ 28 gestational weeks divided by all transferred cycles.

Secondary outcomes

Secondary effectiveness endpoints will include implantation rate, biochemical pregnancy, clinical pregnancy and ongoing pregnancy. *Biochemical pregnancy* will be achieved if serum β -hCG ≥ 10 U/L. *Clinical pregnancy* is defined as the presence of an intrauterine gestational sac 28 ± 4 days after embryo transfer. Ongoing pregnancy is defined as a viable pregnancy at 10-12 gestational week. The safety endpoints will include moderate and severe OHSS, pregnancy loss, pregnancy complications, neonatal birth weight and adverse fetal outcomes (e.g. malformation, intrauterine fetal death, etc.)

Statistical analysis

Sample size and power calculation

Sample size will be calculated based on superiority test. The significance level will be set at $\alpha = 0.05$ and the statistical power will be set as $1 - \beta = 0.80$. The reported live birth rate is about 30%, while the live birth rate of the prolonged protocol is predicted to be around 40% based on previous retrospective studies. We set the delta value as 6%, and the ratio between groups will be 1:1; therefore, the sample size of each group is 851. Taking into consideration a drop rate of 10%, we expect to ultimately have a total of 1892 enrollees, with 946 participants in each group.

Statistical analysis method

1. Statistical description: We will adopt descriptive statistical analysis to summarize the participants' demographic characteristics, physical examination, laboratory tests, other health information and the outcome indicators. The continuous variables will be described with means and standard deviation (or median and interquartile range), while the categorical variable will be described with frequency and percentage. The proportion of drop-off cases will be calculated and analyzed.

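### The primary outcome definition omits the restriction to fresh transfers stated in the design section; read literally it counts frozen cycles, so a woman could enter the denominator more than once

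*Combined protocol and SAP*

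**What the plan says.** All places are in the combined protocol and SAP.

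- **Methods/Design**, on the main comparison: "Their live birth rate of fresh embryo transfer and other secondary outcomes will be compared".
- **Primary outcome**: the endpoint is labelled as a rate per transferred cycle, and the rule for calculating it reads "defined as delivery of any viable infant ≥ 28 gestational weeks divided by all transferred cycles". The definition does not contain the word fresh, does not limit the count to a first transfer, and does not limit it to one outcome per woman.
- **Pregnancy evaluation and follow-up**, last paragraph, immediately before the outcome definitions: "the outcome of frozen-thawed embryo transfer cycles will be followed up and recorded as well". This applies to women who had no fresh transfer and to women without a live birth who still have frozen embryos in store.
- **Trigger and oocyte retrieval**, item 3, describes one route to having no fresh transfer: "there is a high risk of developing moderate or severe OHSS, and all the embryos should be frozen".
- **Sample size and power calculation** gives a total of 1892 and states the group size as follows: "with 946 participants in each group". The unit is the participant.
- **Statistical analysis method**, item 3, assigns logistic regression to categorical outcomes. It does not mention several cycles from one woman.

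No section says whether a frozen-thawed cycle counts in the primary numerator or denominator.

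**The concern.** The design section and the outcome definition do not name the same set of cycles, and the planned data collection will supply the data for both. An analyst working from Methods/Design would leave frozen cycles out. One working from the Primary outcome section would have grounds to put them in.

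The literal reading has three consequences. First, a woman can contribute a further cycle because her fresh transfer failed, so the number of observations depends on the outcome itself. Second, an ordinary logistic regression would treat her cycles as independent. Third, women whose embryos were all frozen are excluded under one reading and can be included under the other. The Background expects the intervention to raise the fresh transfer rate, so the number of such women may differ between the arms.

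At stake is the size of the primary treatment difference, and possibly its statistical significance.

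**Working it through.** **The plan's own figure.** 851 / (1 − 0.10) = 945.6, which rounds up to the stated 946 participants per group. The 851 itself could not be reproduced from the stated rates with standard formulae. That is a separate matter, and nothing below uses the 851.

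**Inputs from the documents.** N = 946 women per arm. Control live birth rate 30%. Intervention rate 40% (the predicted rate), or 36% (30% plus the stated delta of 6%). The documents do not say which denominator these rates refer to; here they are taken as rates per fresh transfer.

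**Inputs assumed, not in the documents.** Fresh transfer rate f = 70% control and 85% intervention. Share of women without a fresh live birth who have one frozen transfer, u = 50%. Live birth rate per frozen transfer q = 35%, taken as equal in both arms. Two-sided 5% test (the plan does not state sidedness), with cycles treated as independent. No dropout.

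**Formulae, per arm**, with p the live birth rate per fresh transfer:
- fresh transfers F = N·f; fresh live births L = F·p
- frozen transfers Z = u·(N − L); frozen live births = q·Z
- fresh-only rate = L/F = p
- all-cycles rate = (L + q·Z)/(F + Z)
- women counted twice = u·(F − L)
- power = Φ[(|p1 − p2| − 1.96·s0)/s1], where s0 is the pooled and s1 the unpooled standard error of the difference

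**Control, 30%.** F = 662.2; L = 198.7; Z = 0.5 × (946 − 198.7) = 373.7; frozen live births 130.8. All-cycles rate = 329.4/1,035.9 = 31.8%. Counted twice: 0.5 × (662.2 − 198.7) ≈ 232.

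**Intervention, 40%.** F = 804.1; L = 321.6; Z = 312.2; frozen live births 109.3. All-cycles rate = 430.9/1,116.3 = 38.6%. Counted twice: about 241.

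**Intervention, 36%.** F = 804.1; L = 289.5; Z = 328.3; frozen live births 114.9. All-cycles rate = 404.4/1,132.4 = 35.7%. Counted twice: about 257.

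| Fresh-only rates | Fresh-only difference | All-cycles rates | All-cycles difference | Power, fresh-only | Power, all cycles |
|---|---|---|---|---|---|
| 30% v 40% | 10 points | 31.8% v 38.6% | 6.8 points | about 98% | about 91% |
| 30% v 36% | 6 points | 31.8% v 35.7% | 3.9 points | about 68% | about 48% |

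**Range.** With f from 70% to 90% varied separately by arm, u from 30% to 70% and q from 25% to 45%, a 6-point difference becomes about 2.5 to 5.2 points and a 10-point difference about 5.0 to 8.6. The difference shrinks in every combination.

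**Equal fresh transfer rates.** With f = 80% in both arms and the other assumptions unchanged, 6 points becomes 4.1 and power goes from about 70% to about 53%. The shrinkage does not need unequal transfer rates.

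**The case against.** The strongest reply is that the documents point to one reading. Methods/Design names fresh transfer. The Background argues from pregnancy in the fresh cycle, the fresh transfer rate and time to pregnancy. Women enter at their first IVF/ICSI cycle. The only transfer procedure described is the fresh day-3 transfer. Frozen outcomes are recorded in addition and are given no role in any endpoint. A sample size in participants fits one fresh cycle per woman. All of this stands, and it makes fresh-only the probable intent. It does not put the restriction into the definition of the primary outcome, which is the text an analyst must follow.

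A reader might infer more than the documents support:
- *That women who fail are counted again.* This follows only on the literal reading, and only for women with surplus embryos who go on to a frozen transfer. Under fresh-only, each woman contributes at most one transfer.
- *That the plan has two equally supported primary outcomes.* It does not; it has a clear general statement and a loosely worded definition.
- *That frozen cycles must dilute the difference because they are handled identically in both arms.* No section describes a frozen-thawed procedure. Equal frozen live birth rates are an assumption of the illustration, and the embryos come from different stimulation protocols.
- *That the sponsor will choose between readings after seeing results.* Nothing says so, and Randomization states that data analysts are blinded. Blinding does not settle the definition, however.

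On size, two limits also stand. At the predicted 30% v 40%, power stays above the planned 80% on either reading. At 30% v 36%, the fresh-only power of 68% is already below 80% on the assumed inputs; only the further fall to about 48% comes from the choice of cycles. The model is also simple: it applies the same frozen uptake to women with all embryos frozen and to women with a failed fresh transfer.

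**Conclusion.** The concern holds in conditional form. The definition of the primary outcome does not carry the fresh-transfer restriction that Methods/Design states, and nothing excludes the frozen cycles recorded under follow-up. If the definition is applied as written, some women contribute more than one cycle to a model with no term for this, in a trial sized by participants.

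The difference between the readings matters most near the plan's own delta of 6 points, where power falls by about 20 percentage points in the base case. If the true difference is 10 points, the estimate shrinks but the trial would still probably detect it. These sizes rest on assumed fresh transfer rates, frozen uptake and an equal frozen live birth rate, and on treating cycles as independent. The gap in the wording rests on none of them.

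Whether the intention-to-treat denominator should be all randomised women is a separate question and is not decided here.

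**What to change.** In the Primary outcome section, replace the open denominator with a definition that matches Methods/Design. For example: live birth at 28 weeks of gestation or later from the first fresh embryo transfer after randomisation, at most one outcome per woman, with frozen-thawed transfers in neither the numerator nor the denominator. Report any result that includes frozen cycles as a separate, named outcome, counted once per woman.

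If the sponsor does intend frozen cycles to count in the primary outcome, the plan must say so before analysis, state how repeat cycles from one woman are handled, and restate the sample size in the matching unit.

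The first option costs one sentence of wording, plus a line for the separate outcome. It needs no new data and no additional participants.

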There are many factors influencing the success rate of IVF/ICSI, e.g. the infertile couples' age, the controlled ovarian hyperstimulation (COH) protocol, the quality and number of embryos for transferring, the endometrium and luteal phase support protocol, etc. Among them, an appropriate COH protocol is directly associated with the number of oocyte retrieved, as well as the number and quality of embryos, which exert an important influence on the success rate of IVF/ICSI. The luteal phase pituitary down-regulation protocol is one of the most widely used COH protocols in clinical practice, particularly in China. In this protocol, gonadotropin releasing hormone agonist (GnRHa) administered in the previous luteal phase induces a state of down regulation of the pituitary gland via competitive occupying and further exhausting the GnRH receptors in the pituitary, which inhibits the endogenous luteinizing hormone (LH) peak and avoid spontaneous ovulation, decreasing the cycle cancellation rate. But the classic down-regulation protocol may lead to an increased incidence of ovarian hyperstimulation syndrome (OHSS), as well as a negative impact on endometrial receptivity due to the progesterone elevation after multiple oocytes development [4]. The coping strategy is to freeze all the embryos and transfer in the next cycle. Though avoiding the above-mentioned adverse effects, such strategy increases the time to pregnancy (TTP) and therefore results in certain psychological and economic burdens for infertile couples.

In recent years, some Chinese researches applied the early follicular full-dose down-regulation protocol that is always performed to women with endometriosis to a more general IVF/ICSI population and found a clinical pregnancy rate of 64% in the fresh embryo transfer cycle, much higher than that of the luteal phase down-regulation protocol [5-10]. The possible mechanism is that it may improve the down regulation of LH and the endometrial receptivity, therefore having a

better control of LH during COH, increasing the endometrial thickness on hCG day, as well as the embryo implantation rate and clinical pregnancy rate. Furthermore, since this protocol decrease the risk of progesterone elevation on hCG day, it increases the fresh embryo transfer rate and shortens TTP.

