Patients will receive luteal phase support with intramuscular progesterone (60mg/day) since the day of oocyte retrieval. On day 3 after oocyte retrieval, two top quality cleavage-stage embryos will be transferred via a catheter under transabdominal ultrasound guidance. The patients will lie in bed for 15 minutes after the procedure. After embryo transfer, 8% progesterone sustained-releasing vaginal gel (Crinone®, Merck, Switzerland) 90mg and dydrogesterone (Duphaston®, AbbottBiologicals, Netherlands) 20mg every day will be used as luteal phase support, continuing for at least 2 weeks. For those who get pregnancy, luteal phase support will be continued to 10 weeks of gestation. The dosage adjustment will be determined by physicians of each study site according to their personal experience.

Pregnancy evaluation and follow-up

All the information will be recorded in our follow-up forms designed specifically for each follow-up visit.

1. *Biochemical determination:* 14 ± 4 days after embryo transfer, serum β -hCG will be tested to determine pregnancy.
2. *Clinical pregnancy determination:* 28 ± 4 days after embryo transfer, a transvaginal ultrasound scan will be performed to confirm the presence of fetal sac, yolk sac and fetal heart.
3. *Ongoing pregnancy determination:* A transvaginal ultrasound scan will be performed at 10-12 weeks of gestation to confirm ongoing pregnancy. The presence of first-trimester pregnancy complications (e.g. OHSS, ectopic pregnancy, miscarriage etc.) will be registered according to the participant's medical record and a telephone follow-up.
4. *28 weeks of gestation:* A telephone follow-up will be conducted to collect the information regarding the second-trimester complications, e.g. pre-eclampsia, gestational diabetes,

prenatal diagnosis, miscarriage, etc.

5. 37 weeks of gestation: A telephone follow-up will be conducted to collect the information regarding the third-trimester complications, e.g. pre-eclampsia, gestational diabetes, preterm birth, etc.
6. *Delivery information:* A telephone follow-up will be made to collect delivery information including gestational age, delivery mode, delivery complications and infant information such as birth weight, any birth defect, etc.
7. *Postpartum information:* Postpartum information includes complications of both the mother and the infant, which will be collected 6 weeks after delivery.

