2. Comparable analysis It will be used to compare the demographic and other baseline characteristics to make sure the comparability of the two groups. If the continuous variables follow the normal distribution, t test will be performed; if not, the rank sum

test or a normal transformation will be performed. For the categorical variables, chi-square test or Fisher's exact test will be performed.

3. Statistical analysis for the outcome measures Between-group differences for categorical and continuous outcome variables will be assessed by logistic regression and linear regression, respectively.
4. Safety analysis: Adverse events and reaction will be listed and analyzed using the chi-square test.
5. The analysis for the primary outcome and important outcome measurements will be based on both the intention-to-treat analysis and per-protocol analysis. The results of these two analyses will be compared in the final analysis.

Reference

- [1] The United Kingdom national data. Human Fertility and Embryology Authority. 2015
- [2] The United States national assisted reproductive technology(ART) data. Centers for Disease Control and Prevention.2015
- [3] Chinese Reproductive Medicine Society national assisted reproductive technology (ART) data. 2015
- [4] L Hu, Y Sun. The impact of various controlled ovarian hyperstimulation (COS) protocols on the outcome of in vitro fertilization and embryo transfer (IVF-ET). *Journal of Practical Obstetrics and Gynecology*. 2014;30(10):723-725.
- [5] Y Hu, T Ding, Y Zhao, Q Wu. The comparison of the birth outcome of in vitro fertilization and embryo transfer (IVF-ET) after two different down-regulation protocols. *Maternal and Child Health Care of China*.2017;32(4):808-810.
- [6] D Xu, Q Wu. The comparison of the application of ultra-long down-regulation protocol and antagonist protocol in in vitro fertilization and embryo transfer (IVF-ET). *Jiangxi Medical Journal*. 2015;50(1):13-15.
- [7] Q Su, Q Wu, L Tian, Y Li. The clinical analysis of different controlled ovarian hyperstimulation (COS) protocols in in vitro fertilization and embryo transfer (IVF-ET). *Jiangxi Medical Journal*. 2014;49(8):723-725.
- [8] Y Li, Q Wu, Y Yi. The impact of the follicular phase ultra-long long down-regulation protocol on PCOS patients' outcome after in vitro fertilization and embryo transfer (IVF-ET). *Jiangxi Medical Journal*. 2014;49(2):117-120.

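### Fresh transfer places two embryos as a rule and the intervention is expected to raise implantation, yet no multiple pregnancy or delivery outcome is named and birth weight has no plurality rule

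*Combined protocol and SAP*

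**What the plan says.** Under Trigger and oocyte retrieval, item 3, the rule for both arms is "Two top-quality Day 3 cleavage embryos will be transferred 72h after retrieval". The section on embryo transfer and luteal phase support repeats it: "two top quality cleavage-stage embryos will be transferred via a catheter under transabdominal ultrasound guidance". The exception is women judged at high risk of moderate or severe OHSS, for whom "all the embryos should be frozen".

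The Background gives the expected mechanism of the intervention as better LH control, "increasing the endometrial thickness on hCG day, as well as the embryo implantation rate and clinical pregnancy rate".

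Under Outcome measurements, the primary outcome is live birth per transferred cycle. Delivery of one or more viable infants at 28 weeks or later is a success, so a twin delivery counts once. The secondary effectiveness endpoints are implantation rate and biochemical, clinical and ongoing pregnancy. The safety endpoints are moderate and severe OHSS, pregnancy loss, "pregnancy complications, neonatal birth weight and adverse fetal outcomes". Multiple pregnancy, multiple delivery and twins appear nowhere in the document.

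For analysis, Statistical analysis method, item 3, says: "Between-group differences for categorical and continuous outcome variables will be assessed by logistic regression and linear regression, respectively". It gives no covariates, strata, subsets or unit of analysis for birth weight.

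**The concern.** When two embryos are placed, a treatment that helps each embryo implant will also more often make both implant. More multiple deliveries are thus the foreseeable cost of the benefit that the trial hopes to show. The primary outcome does not register that cost, the implantation rate credits the second embryo as added benefit, and the safety list does not name it. A trial whose title promises both effectiveness and safety should report it.

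The second issue is birth weight. If the twin share differs between arms, a regression of weight on group over all infants mixes any effect on growth with a difference in twin share. Better standard errors do not help, because the difference lies in the mix of infants and not in its precision. A reader who sees a lower mean in the intervention arm could not tell whether babies grew less or whether there were more twins.

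**Working it through.** The plan gives no figure for multiple birth or birth weight, so there is none to reproduce. What follows is an illustration.

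**Inputs from the protocol (Sample size and power calculation):** live birth about 30% in control and about 40% with the intervention; a delta of 6%, used here for a 30% v 36% case; 851 per group; significance level 0.05, taken as two-sided because the plan does not say. The 851 serves only as a count, and nothing below depends on how it was derived.

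**Assumptions not in the documents:** one fresh two-embryo transfer for each of the 851; a common probability *p* that an embryo leads to a live-born infant; within-woman correlation rho of 0, 0.2 or 0.4, the same in both arms; twins 600-1000 g lighter than singletons; SD 500 g within each plurality; no treatment effect on weight within singletons or within twins; no sibling correlation in the standard error.

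**Step 1, twin deliveries.** P(both) = p² + rho·p(1−p), and live birth L = 2p − P(both). At rho = 0, p = 1 − √(1−L).
- Control: 1 − √0.70 = 0.163; p² = 0.0267, or 22.7 of 851.
- Intervention: 1 − √0.60 = 0.225; p² = 0.0508, or 43.2 of 851.

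This is 2.7% v 5.1% of transfers, or 8.9% v 12.7% of deliveries. Power to detect it as an outcome per woman is about 73% (81% at rho 0.2, 89% at rho 0.4). At 30% v 36% power is 33-48%.

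**Step 2, twin share of infants,** s = 2P(both) / (L + P(both)).
- Control: 0.0533/0.3267 = 16.3%, from 851 × 0.3267 = 278 infants.
- Intervention: 0.1016/0.4508 = 22.5%, from 384 infants.

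**Step 3, shift in the pooled mean.** Shift = gap × (difference in s) = gap × 0.0621, which gives 37, 50 and 62 g for gaps of 600, 800 and 1000 g.

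**Step 4, rejection rate.** The variance per infant is 500² + gap²·s(1−s). At an 800 g gap the SE is √(337,400/278 + 361,700/384) ≈ 46.4 g, so z = 49.7/46.4 = 1.07. Rejection is Φ(1.07−1.96) + Φ(−1.07−1.96) ≈ 18.8%. At 600 g and 1000 g it is 13.7% and 23.7%.

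**Step 5, other inputs** (gap 600-1000 g, SD 500 g):

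| Live birth | rho | Twin share of infants | Shift, g | Rejection |
|---|---|---|---|---|
| 30% v 40% | 0 | 16.3% v 22.5% | 37-62 | 14-24% |
| 30% v 40% | 0.2 | 34.5% v 40.0% | 33-55 | 12-19% |
| 30% v 40% | 0.4 | 52.2% v 56.8% | 27-46 | 10-15% |
| 30% v 36% | 0 | 16.3% v 20.0% | 22-37 | 8-11% |
| 30% v 36% | 0.2 | 34.5% v 37.8% | 19-32 | 7-9% |
| 30% v 36% | 0.4 | 52.2% v 54.9% | 16-27 | 7-8% |

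A common correlation raises the number of twins in both arms but narrows the difference in twin share, so the birth-weight shift falls.

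**The case against.** The strongest reply is that not naming an outcome is different from not reporting it. The endpoint lists are worded as inclusive, and pregnancy complications are left open. On the usual definition of implantation rate (the plan gives none), sacs minus clinical pregnancies approximates the number of multiple pregnancies. Follow-up also collects preterm birth, pre-eclampsia, gestational age and birth weight, through which much of the harm from twins would show. This is fair, and it shows that the data are largely in reach. It does not settle the point: multiple gestation is not among the examples of complications, and preterm birth cannot be attributed to twinning unless plurality is reported.

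Four stronger readings are tempting, and the documents do not support them.
- A reader might infer that every woman receives two embryos. Women at high OHSS risk have all embryos frozen, and no embryo number is given for frozen cycles.
- A reader might infer that the plan prescribes pooling singletons with twins. It is silent. Pooling is what item 3 yields if followed to the letter, but a split or a plurality term is not excluded.
- A reader might infer that the plan manufactures a false harm. On the main assumptions the test still does not reject in 76-86% of trials. A lower mean caused by more twins is also a real consequence of treatment; it misleads only if read as impaired growth, and the plan makes no such claim.
- A reader might take the Background's statement that studies "found a clinical pregnancy rate of 64% in the fresh embryo transfer cycle" as grounds for a much larger shift. That is a clinical pregnancy rate, not a live birth rate, from studies that the protocol describes as mostly retrospective, and no matching control figure is given.

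It is also fair that a singleton-only comparison conditions on something that treatment may change. It therefore belongs beside the overall figure and cannot replace it.

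**Conclusion.** The concern holds in this form: multiple pregnancy and multiple delivery should be named safety outcomes, and birth weight needs a stated plurality rule. The first part needs no birth-weight assumption. It follows from two-embryo transfer, an expected gain in implantation, and a primary outcome that scores twins as one success. Under independent implantation at the plan's predicted rates the omitted outcome would roughly double, from about 23 to 43 women per 851, a difference that the trial could plausibly detect.

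The birth-weight part is smaller. The most adverse of the scenarios tabulated gives a 62 g shift and 24% rejection at a nominal 5%, and the mildest gives 16 g and 7%. A misleading signal is possible but not likely. The gap, SD and correlation are assumed, and fewer than 851 fresh transfers per arm would change the counts. The primary analysis is not affected.

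**What to change.** - **Outcome measurements:** add multiple pregnancy (sac count at the 28±4 day scan) and multiple delivery to the safety endpoints, each reported per randomised woman and per transfer.
- **Pregnancy evaluation and follow-up:** record the number of infants explicitly at the delivery call.
- **Statistical analysis method, item 3:** report birth weight separately for singletons and twins, with singletons as the main comparison of fetal growth, alongside the overall figure. Allow for sibling correlation wherever twins are included.

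The cost is mainly wording, because the scan and the delivery call are already planned, and no treatment or transfer rule changes. The downside is fewer infants in each comparison. Both comparisons are also conditional on post-randomisation outcomes (live birth and plurality), which the report must state.
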